2.4. Data and Safety Monitoring Plan

The PIs and research staff will conduct ongoing monitoring the progress of this pilot intervention trial and the participant safety. This Data and Safety Monitoring Plan will be used to assess on-going participant safety. No invasive procedure will be used in the study. The participants will be fully informed of the procedures, including notification that their medical records from the DVAMC will be examined. Participants will voluntarily sign an Informed Consent and HIPAA Authorization approved by the DVAMC IRB before participation begins.

Data will be collected from the participants by face-to-face interview, having them complete objective psychometric instruments such as questionnaires and validated tests, and *via* the widely used procedure of HRV Biofeedback. In addition, data will be collected by record review of medical and service history obtainable from the Dorn VAMC Electronic Medical Record (CPRS), after authorization has been signed by the patient. Data collection will be specifically for the proposed research. Data collection time points for HRV and questionnaire will be at pre-training (T-1), post-training (T-2), 4-week post-training booster (T-3), and 8-week post-training follow-up (T-4). Baseline measurements will occur after the patient has been screened for eligibility, and consented. Randomization will occur after baseline assessment. All variables will be measured at each time point except demographics (T-1 only), and saliva (T-1, T-2, T-4). Measurements will be the same for both the active and sham intervention groups.

Potential Benefits. This study is designed to elicit relief from pain and related symptoms, although the study it is an experimental intervention and subjects may not obtain direct personal benefit. However, benefit to future patients is possible. Patients will receive an acknowledgement of their time and effort in participating in the study and they will receive financial compensation for each assessment and training session according to the schedule of incentives. The knowledge generated by this study will provide an understanding of the potential benefit of HRV-B on pain, stress, fatigue, sleep and quality of life for Veterans with chronic pain, and may inform clinical practice and programmatic standards concerning appropriate ways to assist with pain management, sleep disturbance and fatigue among DVAMC patients.

Potential Risks. No significant physical, social, or legal risk is anticipated with this study. All proposed procedures have been widely used over a long period of time by the investigators and/or others. HRV-B is a noninvasive procedure. There have been a few cases of relaxation-induced anxiety noted (i.e., with progressive muscle relaxation), but these effects are not associated with HRV-B or controlled breathing. Other negative reactions that have been associated with other modalities of biofeedback-assisted relaxation (such as sensation of heaviness, feelings of sadness, disturbing thoughts, or mind wandering) are rare, mild, and brief. All these reactions can be prevented by an experienced biofeedback professional with precautions, patient education, and careful monitoring.

Risks to confidentiality are minimal since all data will be coded with a study ID. Study ID and patient list will be kept separate, and the file linking study IDs with personal identifiers will be maintained in a locked file cabinet of password protected electronic file in one or both of the PI's offices. Data safety and monitoring is described below.

No adverse events were observed during other HRV-B studies. . Subjects will be informed that the experimental protocol will be provided in addition to their treatment as usual, will not affect their usual care, and no other intervention is available as an alternative intervention at the DVAMC. Minimal risks are anticipated for the subjects.

Protection Against Risks. Veterans seeking care at the DVAMC who meet the eligibility criteria will be recruited for participation according to applicable laws, regulations, guidelines, and policies protecting privacy and

confidentiality, and not until after a HIPAA Waiver of Authorization is approved by the IRB and R&D Committees. Following IRB and R&D Committee approvals, recruitment will be initiated among patients in the DVAMC Pain Clinic. If accrual milestones are not met, we will expand our search for eligible patients to include the DVAMC Rehabilitative Medicine and Rheumatology departments.

A waiver for release of protected health information will be requested to obtain the name, address, phone number, and screening information for patients with scheduled appointments in the Pain Clinic, or Rehabilitative Medicine or Rheumatology departments. The use and destruction of this data will follow the policies and procedures of VA privacy regulations. After receiving the authorization, the recruitment plan described in Section 2.1 will be used. Confidentiality will be maintained to the fullest extent allowed by law. Only authorized personnel will have access to research data. Participants will receive a unique study ID number that will be used to track all data. The cross-reference file linking subject identities to the study ID number will be maintained in a locked file cabinet or password-protected VA computer by the Co-PIs or a designated staff member. Psychophysiological data collected by sensors will be stored electronically without any identifying information. Analysis and interpretation of data files also will be conducted without the use of personal identifying information. Questionnaire data will not have identifying information on the forms. Once collated, coded data will be entered into password-protected VA computer for further analysis and processing.

If patients exhibit excessive anxiety, research staff will check with the patient to ascertain if data collection needs to be temporarily discontinued or rescheduled. Adverse physical or psychological events sometimes occur even if they are not directly related to the study protocol. If a participant experiences a major or minor physical or psychological adverse event while enrolled in this study, supportive measures described in the section of the consent form labeled 'possible risks' in will be implemented. The Co-PIs will be contacted immediately. The PI will consult with clinical support staff to refer the patient for appropriate follow-up care, if needed..

Adverse Event Reporting. If patients develop a severe affective disorder or psychosis, these will be considered a serious adverse experience. The PIs will send an adverse events report to the VA IRB as soon as they are apprised that an adverse event has occurred. If the VA IRB or either of the PI's recommend that the study be temporarily or permanently suspended, this action will be reported to the VA grant program officer or director.

Data and Safety Monitoring. The PIs and research staff will routinely monitor the progress of the trial and the safety of participants. The PIs, in collaboration with study staff, will check accrual and attrition on a weekly basis. Subject eligibility forms will be completed on all participants to assure appropriate subjects are recruited. None of the study procedures are considered invasive and the risks to subjects are expected to be minimal. Subjects will be informed that the experimental protocol will be provided in addition to their usual care, will not affect their treatment as usual, and no other intervention is available as an alternative intervention. HRV-B training is a simple, non-invasive procedure and no major adverse reactions to the protocol are anticipated. The proposed procedures have been widely used; no adverse events were experienced by [name] in previous studies using HRV-B or actigraphy. Questionnaire data will be collected from the participants by face-to-face interview using validated instruments and questions that are similar to those that might be encountered in a clinical setting. Participants will be informed that if they don't want to answer a question, they can skip it. An actiwatch is similar in size, weight, and configuration as a wristwatch. Saliva collection also is simple and non-invasive. Saliva biospecimens will be labeled in a manner that ensures participant confidentiality without personal identifiers. The participants will be fully informed of the procedures, including notification that their medical records will be examined. Participants will voluntarily sign an Informed Consent document and HIPAA Authorization approved by the IRB before participation begins.

We are planning a follow-up HRV-B session plus questionnaire and cognitive evaluation at 4 weeks and 8 weeks post-training (Figure 7). Subjects will be told that they may contact either PI for any reason for 6 months after this final follow-up session. Subjects will be encouraged to make contact during this 6 month post-follow-up period if they have questions, or if any problem arises that the subject believes may be related to this research. If, during the course of the protocol, any adverse reaction develops or a subject wishes to terminate

his or her participation, the assigned treatment will be stopped. We will encourage any patients who have their assigned treatment stopped to maintain attendance at their training visits even without treatment, and attempt to collect the evaluation data on the appropriate schedule. Follow-up would be stopped if the subject advises us that he or she wishes to terminate all participation in the research. During the consent process, the subject will be told that cessation of follow-up can be voluntarily obtained by signing a form requesting that no further contact be made. They also will be informed that termination of their participation will not impact their usual care at the DVAMC.

The DVAMC uses a Research Compliance Officer (RCO) as the clinical trial monitor who performs audits of consent forms, reporting and regulatory compliance, and documentation according to Standard Operating Procedures of the VA Office of Research and Development, and the local DVAMC Research office. The monitor reports separately from the IRB structure. The monitor will also perform random audits on any trial including the proposed study.

Data Accuracy and Protocol Compliance. Subject eligibility forms will be completed on all subjects to assure appropriate subjects are recruited. Biofeedback Certification Institute of America (BCIA) certification of training and skill in HRV-B or its equivalent will be required of the HRV-B professional. This research will follow the HRV-B training protocol adopted by the BCIA. Protocol compliance integrity will be monitored by supervision and communication between the biofeedback professional, research staff, and the Co-PIs.

Literature Cited

1. Simon LS. Relieving pain in America: A blueprint for transforming prevention, care, education, and research. *Journal of Pain and Palliative Care Pharmacotherapy*. 2012;26(2):197-198.

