1.2. Specific Aims

This study fulfills the national VHA/DoD Task Force recommendation that complementary, integrative therapies for pain management be provided to Veterans. Chronic pain elicits stress which increases sympathetic output fostering autonomic nervous system imbalance, an overextended stress response, fatigue, depression and insomnia. Heart Rate Variability (HRV) is a measure of the interplay between the sympathetic and parasympathetic nervous systems, and thus is a useful and easily-measured index of autonomic balance that has a relationship to chronic pain effects. HRV biofeedback (HRV-B) is a novel, biobehavioral procedure that restores normal autonomic balance. Through HRV-B, patients increase parasympathetic cardiac output and restore autonomic balance via induction of 'HRV coherence'. Our pilot study indicated that HRV-B produced coherence and alleviated self-reported ratings of chronic pain and stress among Veterans attending our Pain Clinic.⁵⁰ The proposed clinical intervention will further test hypotheses that HRV-B increases HRV coherence, reduces self-reported pain, stress, depression, fatigue, and insomnia, and improves cognition among Veterans with chronic pain.

The **specific aims** are to: (1) conduct a randomized, sham-controlled, pilot intervention trial to determine whether HRV-B increases HRV coherence among chronic pain patients (n=40 each for the HRV-B and sham treatment groups; total N=80 patients); (2) determine whether HRV-B reduces self-reported pain and stress among chronic pain patients. The primary endpoints include HRV coherence, pain (Brief Pain Inventory or BPI), and stress (Perceived Stress Scale or PSS).

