Random Assignment to the 6-week HRV-B treatment or sham intervention group will occur following the baseline assessment. We will use a permuted block randomization procedure, with a block size of 4 and no stratification. Thus, for example, assuming 20 patients are to be assigned either to Sham (S) or Biofeedback, there would be 20 blocks of 4 patients, and two patients will be assigned each to the (S) treatment and two to the biofeedback by randomly selecting one of six possible permutations of the two treatments in blocks of four. The order of the blocks will be randomly generated. The treatment assignment will be determined before any patient is enrolled into the study and the documentation and assignment of patients will be kept confidential and known only to the PI ([name]). Only the Biofeedback professional, who delivers the treatment, will know the treatment status of the participant; other study personnel will be blinded to treatment status.

HRV-B Training. HRV-B training will follow our previously established, standardized protocol that is consistent with recommendations of the Biofeedback Certification Institute of America (BCIA), consisting of a 15-minute resting period that includes HRV recording, and a 25-minute biofeedback training and coaching or sham period. The resting periods are the same for both the HRV-B treatment and sham groups. Participants will be affixed with HRV monitoring equipment and will be instructed to sit quietly for 15 minutes in a relaxed posture, viewing a static nature scene on a computer monitor, without any instruction, coaching or biofeedback. Coaching or instruction will start after the 15-minute resting period. Patients in the sham condition will be asked to 'just relax' or 'take it easy' for the remainder of the 25-minute session. Patients in the HRV-B group will be coached on how to achieve HRV coherence.

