effects of home practice. Information will be solicited in the questionnaire regarding the factors that contributed to or detracted from home practice for inclusion in the analysis. One goal of this intervention is to spontaneously and consistently achieve HRV coherence on demand outside a clinical environment. Therefore, participants will be provided with a portable colorimetric finger PPG (emWave® hand held personal stress reliever; dimensions similar to a cell phone; weight: 2.2 ounces) for home practice and use between weekly HRV-B training sessions. Home HRV-B practice period data from the device can be compared to self-report and further analyzed with regard to the outcomes (see Appendix III, IV).

Intervention Integrity. Several procedures will be used to evaluate treatment integrity. The intervention will follow the HRV-B protocol adopted by the BCIA, and BCIA certification for HRV-B or its equivalent training will be required for trainers in this study. Protocol compliance integrity will be monitored and supervised by research staff and [name], and via communication between them and the certified biofeedback professional ([name]). We will ask patients about whether they thought they were enrolled in the active or control condition. We will then summarize these data along with the number and duration of participant visits over time, and compare these values between the sham and treatment groups. Contrasts between the sham and treatment condition for outcomes measured at baseline, post-treatment, booster, and at the 8-week follow-up will allow us to evaluate the accuracy and delivery of the intervention. Measures of HRV coherence will allow for direct, quantitative assessment of participant performance and receipt of intervention.

Sham Treatment. To control for the laboratory environment or other placebo effects, participants assigned to the sham HRV-B training group will be scheduled by the biofeedback professional for a weekly clinic meeting during the 6-week period of the project that matches the timing and duration of the active HRV-B sessions. The sham procedure has been used successfully in our ongoing study of HRV-B among PTSD patients for the past three years. During these lab visits, sham training participants will have their heart rate, respiration, blood pressure and blood pressure volume recorded during a 15-minute resting period, but no active training or coaching will be provided.

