During the ~25 minute coaching period, the Biofeedback professional has the participant sit quietly in front of the computer screen with the fingertip PPG in place, but the recording input is switched off so no information on heart rate is delivered to the recording equipment. No active biofeedback coaching is delivered regarding resonant frequency breathing, imagery, or positive emotion induction. The Biofeedback professional uses passive relaxation statements such as: 'try to relax' and 'please sit quietly' during the coaching period. During the passive 15-minute HRV recording period after the coaching session, the recording input of the PPG is switched on, and the subjects view the same static relaxing nature scene on the monitor as is presented to the HRV-B group. For home practice, participants in the sham group are given a 'squeeze stress ball' and asked to use it throughout the normal activities of the day. Subjects in the sham group will be asked to self-report the frequency and duration of squeeze ball use.

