Primary & Exploratory Questionnaire Outcomes. In addition to HRV coherence, the primary outcomes (pain, stress), as well as the related exploratory measure, will be assessed at baseline, after the 6-week intervention period, during the booster session and at the follow-up session. Validated instruments will be used to administer a structured questionnaire focusing on: 1). pain (BPI^{64,65}) and stress (PSS⁶⁶); 2). the exploratory outcomes (sleep, fatigue, depressive symptoms, cognitive performance); 3). well-being (coping, social support); 4). lifestyle (chronotype, social jetlag); 5). socio-demographic and personal characteristics (age, height, weight, education, income, physical activity); 6). occupation (current or previous job title, combat history, shift work); 7). supplemental use of pain medications including over the counter anti-inflammatory agents [e.g., NSAIDs], as well as alcohol and tobacco consumption; and 8). whether they have a pending worker compensation claim or personal injury litigation related to their pain or other symptoms. Some items from the medical record (e.g., age, body weight) will be compared with questionnaire data to assess reporting validity. Questions focusing on the duration of symptoms (e.g., sleep disruption, fatigue) will be integrated into the study instrument (e.g., the duration of: sadness, fatigue, stress, or sleep disruption). Co-morbid diagnoses of: hypertension, diabetes, cardiovascular disease, stroke, obstructive sleep apnea or other sleep disorders, or

post-traumatic stress disorder (PTSD), and use of prescription medications (hypnotics and other sleep aids, antidepressants, anxiolytics), and will be assessed by chart review after obtaining a HIPAA release of medical information as part of the informed consent process. Questionnaires are presented in Appendix V.

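### Pain and stress scores are to be collected by interview, in a questionnaire that also asks about home practice with arm-specific tools, so staff who are meant to be blinded may learn the arm

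*Combined protocol and SAP*

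**What the plan says.** All references are to the combined protocol and SAP.

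- **Blinding.** The opening summary concedes that patients are difficult to blind and that the coach must know the arm, and says that everyone else is blinded. Section 2.2 (Random Assignment) has the PI hold the assignments, has the biofeedback professional know them, and says that "other study personnel will be blinded to treatment status".
- **Outcomes.** Section 1.2: "The primary endpoints include HRV coherence, pain (Brief Pain Inventory or BPI), and stress (Perceived Stress Scale or PSS". Section 2.2 (Primary & Exploratory Questionnaire Outcomes): "Validated instruments will be used to administer a structured questionnaire focusing on: 1). pain", with stress in the same item.
- **Mode of collection.** Section 2.4 (Data and Safety Monitoring): "Questionnaire data will be collected from the participants by face-to-face interview using validated instruments and questions". The opening of Section 2.2 also has study staff interview patients for the baseline primary outcomes. Earlier in Section 2.4, however, interview is listed together with "having them complete objective psychometric instruments such as questionnaires and validated tests". Section 2.2 describes the PSQI as self-administered and the BDI-II as self-report.
- **Home practice.** Section 2.2 (Home Practice): "Information will be solicited in the questionnaire regarding the factors that contributed" to home practice or detracted from it. According to the opening summary and Section 2.2 (Sham Treatment), the active arm practises with a hand-held device and the sham arm is given a squeeze ball. "Subjects in the sham group will be asked to self-report the frequency and duration of squeeze ball use".
- **Treatment guess.** Section 2.2 (Intervention Integrity): "We will ask patients about whether they thought they were enrolled in the active or control condition". No corresponding question is planned for assessors.

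**The concern.** BPI and PSS are subjective. With patients hard to blind, staff blinding is one of the few protections left for these scores. A person who knows the arm can, without intending to, affect how a question is put, how far an answer is probed and what is written down. The same applies to the two cognitive tests that a person gives and scores, the PASAT and the Hopkins test. The plan claims blinded staff, but it puts questions whose natural answers may name the practice tool into the questionnaire that carries the primary scales. It says nothing about order, separation or disclosure.

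**Working it through.** **Step 1: set the passages side by side.**

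| Link | Where | What is established |
|---|---|---|
| Staff other than the coach and the PI are blinded | Opening summary; 2.2 Random Assignment | Stated |
| BPI and PSS are in the structured questionnaire | 2.2 Questionnaire Outcomes | Stated |
| Questionnaire data come from face-to-face interview | 2.4 Data and Safety Monitoring | Stated, but qualified earlier in 2.4 and by the PSQI and BDI-II descriptions |
| Home-practice items are in the questionnaire | 2.2 Home Practice | Stated, although the eight-part content list in 2.2 omits them |
| The practice tool differs by arm | Opening summary; 2.2 Sham Treatment | Stated |
| Squeeze-ball use and treatment guess are asked in the same interview | 2.2 | Not stated: no form, recipient or timing is given |
| Item order, non-disclosure rule, check of assessor blinding | – | Not found |
| Who collects post-baseline questionnaires | – | Not named |

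The point needs only the first five links. The squeeze-ball report and the treatment guess would add to the exposure if they are asked in the interview, but the point does not depend on them.

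**Step 2: how much data is exposed.** Randomisation follows baseline, so the arm cannot be revealed at T-1. The exposed assessments are T-2, T-3 and T-4. With 80 patients this is at most 80 × 3 = 240 questionnaire administrations. Of the five outcomes in Table 3 of Section 2.3, four (pain rating, negative emotion, activity limitation, perceived stress) are questionnaire scores. The fifth, HRV coherence, is computed from sensor recordings.

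**Step 3: does the power calculation bear on it?** Power for a two-sided two-sample t-test at α = 0.01 is 1 − F(t*; df, δ) + F(−t*; df, δ). Here F is the noncentral t distribution function, t* the critical value, df = 2n − 2 and δ = difference / (SD × √(2/n)).

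- Perceived stress: difference 4 − (−1.2) = 5.2, SD 4.5. At n = 25 per group, δ = 5.2/(4.5 × 0.2828) = 4.09 and power is 91.42% (plan: 91.4%). At n = 40, δ = 5.2/(4.5 × 0.2236) = 5.17 and power is 99.34% (plan: 99.3%).
- Pain: difference 10 − 1.8 = 8.2, SD 5.0. At n = 25, δ = 5.80 and power is 99.87% (plan: 99.9%).

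The plan's figures reproduce, and none is disputed.

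**Step 4: illustration only.** The documents give no size for interviewer bias, so b below is an assumption. Suppose there is no true effect and recording shifts the difference between arms by b standard deviations. Then δ = b/√(2/n), and the chance of p < 0.01 is:

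| b (SD) | Pain points (b × 5.0) | PSS points (b × 4.5) | n = 25 per group | n = 40 per group |
|---|---|---|---|---|
| 0 | 0 | 0 | 1.00% | 1.00% |
| 0.1 | 0.5 | 0.45 | 1.45% | 1.75% |
| 0.2 | 1.0 | 0.90 | 2.98% | 4.48% |
| 0.3 | 1.5 | 1.35 | 6.06% | 10.34% |

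The larger sample makes a given bias more likely to reach significance, so ample power gives no protection. The table does not show that a bias of any of these sizes will occur.

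**The case against.** The strongest reply is that interviewer recording of BPI and PSS is not established. The interview sentence sits in a safety section about participant burden. The same section also speaks of participants completing instruments, at least two scales are described as self-completed, and pain and stress are called self-reported throughout. This stands in part. The mode is ambiguous, and self-completion would largely remove the recording route. But no passage says that BPI or PSS is self-completed, and the opening of Section 2.2 and its questionnaire paragraph point towards staff administration.

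A reader might go further and infer that assessor blinding must fail for every patient at every follow-up visit. The documents do not support that. A patient asked what hindered practice may say only that there was no time. Squeeze-ball use may go into the daily log that both groups keep. A patient's guess is not disclosure of the arm. If the practice items come last, that visit's scores are already recorded. The questionnaires (Appendix V) could not be checked for wording or order.

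It is also fair that patients who recognise their arm may bias their own answers whoever asks. That issue is separate and would remain after any fix here. Finally, the PASAT and Hopkins scores are counts of correct answers or recalled words, which leaves less room for influence than a rating scale.

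**Conclusion.** The point holds as a risk that the plan creates and does not control. As written, an interviewer who is meant to be blinded may learn the arm at T-2, T-3 or T-4, before or while recording BPI and PSS or giving the cognitive tests. Disclosure is likely in some patients; that it happens in all of them, or that blinding cannot hold, is not shown. The size of any bias is unknown, and HRV coherence is much less exposed.

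The conclusion rests on three assumptions:

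- the interview statement in Section 2.4 applies to BPI and PSS;
- the home-practice items are asked at one or more post-baseline assessments, which the plan does not specify;
- the forms do not already separate these items.

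If the second or third is wrong, a sentence in the protocol saying so would settle most of the matter. If the first is wrong, the recording route for BPI and PSS falls away, and the interview wording needs correcting. The change is worth making because it is cheap and supports a blinding claim that the trial will rely on.

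**What to change.** Amend Section 2.2 (Primary & Exploratory Questionnaire Outcomes) and both descriptions of data collection in Section 2.4 so that they agree:

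1. State that patients self-complete BPI, PSS and the other self-report scales as the first step of each assessment visit, and that named blinded staff then give the cognitive tests.
2. Move home-practice, squeeze-ball and treatment-guess items to a separate self-completed form given after all outcomes. Have it returned sealed or coded so that neither the assessor nor the coach sees the treatment guess. The coach should not collect the guess, because the coach knows the arm and could influence the answer.
3. Ask patients not to mention their practice tool to the assessor or bring it to the assessment.

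The cost is one split form, a fixed visit order and possibly slightly more missing items than under interview. A completeness check that does not involve discussing answers would reduce the missing items. Endpoints, sample size and both interventions are unchanged.
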